8. END OF STUDY

End of the study will be marked by the last patient's last visit samples when they have been analysed. The data will then be scrutinised, and finally an article summarising the study written and submitted to a peer-reviewed journal for consideration of publication. Positive trial results might lead to implementation of the use of intravenous Cangrelor in clinical practice.

Study termination

The safety monitoring committee/Steering Committee will meet on a regular basis. The trial will be terminated early if there is evidence of unexpected excess bleeding with cangrelor or severe or unexpected complications from the IMR procedure.

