9. ADVERSE EVENTS

9.1 **DEFINITIONS**

9.1.1 Adverse Event (AE): any untoward medical occurrence in a patient or clinical study subject. Adverse events will stop being recorded after 36 hours from the index admission.

9.1.2 Serious Adverse Event (SAE): any untoward and unexpected medical occurrence or effect that:

- Results in death
- Is life-threatening refers to an event in which the subject was at risk of death at the time of the event; it does not refer to an event which hypothetically might have caused death if it were more severe
- Requires hospitalisation, or prolongation of existing inpatients' hospitalisation
- Results in persistent or significant disability or incapacity
- Is a congenital anomaly or birth defect

Common expected post-procedural adverse events listed below are the conditions not going to be classed as SAEs:

- Acute renal failure requiring haemodialysis, peritoneal dialysis or haemofiltration
- Ventricular arrhythmia requiring direct-current (DC) cardioversion
- Atrial arrhythmia requiring intervention
- Significant heart block requiring temporary or permanent pacing
- Cardiac tamponade requiring urgent surgical intervention
- Cardiogenic shock requiring intra-aortic balloon pump or other assist device
- Emergency coronary artery bypass graft operation

- Arterial complications
- Blood or platelet transfusion

Medical judgement should be exercised in deciding whether an AE is serious in other situations. Important AEs that are not immediately life-threatening or do not result in death or hospitalisation but may jeopardise the subject or may require intervention to prevent one of the other outcomes listed in the definition above, should also be considered serious.

9.2 **REPORTING PROCEDURES**

All serious adverse events will be reported. Depending on the nature of the event the reporting procedures below will be followed. Any questions concerning serious adverse events reporting will be directed to the Chief Investigator in the first instance.w3433;

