9.2.2 Serious AEs

An SAE form will be completed and faxed to the Chief Investigator within 24 hours. However hospitalisations for elective treatment of a pre-existing condition do not need reporting as SAEs. Information about all serious adverse events will be collected and recorded on the Serious Adverse Event Report Form and faxed to the R&D Directorate at New Cross Hospital within 24 hours of learning of its occurrence.

All serious adverse events will be reported to the appropriate regulatory and ethical authorities.

Contact details for reporting SAEs [contact], attention [name] Please send SAE forms to: [name] [contact] (Mon to Fri 09.00 – 17.00)

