11.2 SAFETY AND DATA MONITORING

Due to the nature of the study, data monitoring committee will not be required.

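### Section 9.1.2 makes SAE status depend on being unexpected and exempts nine event types, so a severe but expected IMR complication meets the section 8 stopping rule yet misses 24-hour reporting

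*Combined protocol and SAP*

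**What the plan says.** All references are to the combined protocol and SAP.

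- **SAE definition (9.1.2).** An SAE is "any untoward and unexpected medical occurrence or effect" that meets one of five criteria: death, threat to life, new or longer hospital stay, lasting disability, or congenital anomaly.
- **Exemptions (9.1.2).** Nine conditions follow the sentence "Common expected post-procedural adverse events listed below are the conditions not going to be classed as SAEs". They include "Cardiac tamponade requiring urgent surgical intervention", "Arterial complications" (with no severity limit) and "Blood or platelet transfusion".
- **Adverse events (9.1.1, 9.2.1).** The AE definition has no expectedness condition. Non-serious AEs are all recorded, expected or not. Recording ends 36 hours after index admission.
- **SAE reporting (9.2.2).** An SAE form goes to the Chief Investigator and to the R&D Directorate within 24 hours. The section adds: "All serious adverse events will be reported to the appropriate regulatory and ethical authorities".
- **Stopping rule (8).** A safety monitoring or steering committee meets regularly. The trial ends early on bleeding with cangrelor that is both excessive and unexpected, or on "severe or unexpected complications from the IMR procedure".
- **Monitoring (11.2).** "Due to the nature of the study, data monitoring committee will not be required".
- **Safety endpoints (4.2).** BARC bleeding, target vessel failure and vital status at discharge.

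**The concern.** Seriousness describes how bad an event is. Expectedness describes whether it was foreseen, and normally decides only how quickly outside authorities are told. Section 9.1.2 makes the first depend on the second. Read literally, a foreseen death or life-threatening event is not an SAE, and nine conditions can never be one, however severe.

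Section 8 uses a different test. Its IMR trigger is met by a complication that is severe *or* unexpected. A severe, foreseen complication is therefore grounds for ending the trial but stays outside the only reporting route with a deadline. The committee applying the rule could hear of it late, or only if someone chooses to tabulate AEs for it.

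**Working it through.** No formula applies. The documents give no bleeding rate, IMR complication rate or stopping threshold. The check sets the definitions against the stopping rule and traces where each exempt event would still be recorded.

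**Step 1. The two tests side by side, for an IMR complication that meets a seriousness criterion.**

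| Complication | Meets section 8 trigger? | SAE under 9.1.2? |
|---|---|---|
| Severe, unexpected, not listed | Yes | Yes |
| Severe, expected | Yes | No |
| Severe, one of the nine listed types | Yes | No |

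The second and third rows are the conflict. The discretion clause at the end of 9.1.2 does not clearly resolve it, because it covers situations other than those already dealt with. It also sits awkwardly with the list: it treats an event that may need intervention to avert a serious outcome as serious, while listed events that have already needed surgery, pacing or cardioversion are not.

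**Step 2. Where each exempt type is still recorded.** All nine remain AEs to 36 hours. This assumes that an event denied SAE status is handled as non-serious under 9.2.1. Beyond that:

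| Exempt type | Other named source |
|---|---|
| Tamponade needing surgery | BARC type 3b |
| Transfusion | BARC type 3a, if with overt bleeding |
| Arterial complications | BARC, if bleeding |
| Emergency bypass surgery | BARC type 4, if the bleeding criteria are met |
| Renal failure needing dialysis or filtration | None |
| Ventricular arrhythmia needing cardioversion | None |
| Atrial arrhythmia needing intervention | None |
| Heart block needing pacing | None |
| Cardiogenic shock needing a support device | None |

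BARC covers one type outright and three conditionally, so 9 − 4 = 5 types rest on AE recording alone. Two general sources could add to this. Vital status catches deaths. Target vessel failure may catch some events, but the protocol does not define it, so which ones cannot be settled.

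**Step 3. Time.** Appendix 2 schedules AE review at its first six timepoints, stopping at 36 hours, with none at discharge or three months. Acute harm from the wire or the adenosine infusion falls inside that window. A listed non-bleeding event after 36 hours has no clear stated capture unless it is fatal or counts as target vessel failure. As the table was extracted, it marks BARC only at the end of PPCI, although section 4.2 calls it an in-patient endpoint.

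**Step 4. IMR.** Section 6.6 adds a pressure wire in the culprit artery and intravenous adenosine. The study costs budget 100 wires for 100 patients, so both arms of 50 are exposed by design. Comparing arms therefore cannot show harm from IMR itself. Only attribution of individual events can, and no attribution or timing item is described. None of the three endpoints in section 4.2 is specific to IMR.

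**Step 5. Route to the committee.** Section 8 does not say what the committee receives. Section 9.2.2 names the Chief Investigator, the R&D Directorate and the authorities, but not the committee.

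**The case against.** The strongest reply is that nothing disappears. A reader might infer that the stopping rule has no data to work from, or that the committee could see no signal because the definition removed it. The documents do not support that. Exempt events remain AEs, AEs are recorded whether expected or not, and review is scheduled through the procedure and up to 36 hours. For bleeding the inference is weaker still: BARC is collected regardless of SAE class, and its type 3 includes tamponade and transfusion with overt bleeding. This part of the reply stands.

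Three further points carry weight:

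- The protocol lists no IMR complications, and section 10.2 calls the added risk negligible. It cannot be assumed that IMR harm would take only the listed forms. An unlisted, unexpected event that meets a criterion is still an SAE.
- Not every listed event is serious. Arterial complications have no severity limit, and a transfusion need not meet any of the five criteria.
- A reader might take sections 8 and 11.2 as a flat contradiction. They may refer to different bodies, so what can be shown is an unclear remit.

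The reply does not answer the mismatch in Step 1, the absence of a stated route to the committee, or the 36-hour limit.

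**Conclusion.** The point holds as a defect in classification and reporting. It does not hold as a wholesale loss of safety data. Section 9.1.2 conflicts with the IMR trigger in section 8. Expected events and the nine listed types bypass 24-hour reporting, and no route takes them to the committee that applies the rule. Five of the nine types depend on AE recording alone, apart from vital status and the undefined target vessel failure endpoint. The gap is greatest for IMR, and least for bleeding.

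The number of patients affected cannot be stated, because the documents give no rate for any listed event. The conclusion rests on two readings: that *unexpected* in 9.1.2 is meant literally, which the exemption list supports, and that exempt events are handled as AEs under 9.2.1. This is a stated rule that works against patient safety and is cheap to reword, so it should be changed.

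**What to change.** 1. In 9.1.2, delete *and unexpected*. Class a listed event as an SAE whenever it meets a seriousness criterion.
2. Record expectedness, and timing relative to IMR (before, during or after), as separate fields on the event form.
3. Amend 9.2.2 so that every SAE reaches the Chief Investigator and the R&D Directorate within 24 hours, with expectedness used only to decide expedited reporting to the authorities. Without this edit, the present wording would send every reclassified event to the authorities.
4. State in section 8 that the committee receives SAE counts and BARC bleeding by arm, and IMR-related events for both arms together. Reconcile this with 11.2 by saying which body is meant.
5. Say whether the 36-hour limit in 9.1.1 also applies to SAEs.

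The cost is revised wording, a few added fields and more SAE forms, with no new committee or staff. Section 5.6 names an SAE as one possible ground for withdrawing a participant, so it should be checked against the wider definition.

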9.2.1 Non serious AEs

All such events, whether expected or not, will be recorded.

9.2.2 Serious AEs

An SAE form will be completed and faxed to the Chief Investigator within 24 hours. However hospitalisations for elective treatment of a pre-existing condition do not need reporting as SAEs. Information about all serious adverse events will be collected and recorded on the Serious Adverse Event Report Form and faxed to the R&D Directorate at New Cross Hospital within 24 hours of learning of its occurrence.

All serious adverse events will be reported to the appropriate regulatory and ethical authorities.

Contact details for reporting SAEs [contact], attention [name] Please send SAE forms to: [name] [contact] (Mon to Fri 09.00 – 17.00)

10 ETHICAL CONSIDERATIONS

10.1 Review by an NHS Research Ethics Committee

Ethics review of the protocol for the trial and other trial related essential documents (e.g. patient information sheet, consent form...) will be carried out by a UK Research Ethics Committee (REC). Any amendments to these documents, after a favourable opinion from the REC has been given, will be submitted to the REC for approval prior to implementation.

10.2 Potential Risks and Benefits of Participation

Potential Benefits to Participants: CMR clinical report will be generated and available to clinical care team with assessment of LV function and infarct characteristics that may guide future management.

Potential Harms to Participants: The magnetic fields and radio waves used in cardiac MRI have no side effects. This method of taking pictures of organs and tissues doesn't carry a risk of causing cancer

or birth defects. There is a small risk of side effects due to contrast administration during CMR. Gadolinium contrast medium is generally very safe. Side effects or reactions are uncommon but may occur. The most common adverse reactions are brief headache, nausea (feeling sick) and dizziness for a brief time following the injection. This occurs in 1% to 5% of contrast injections. Infrequently, a feeling of coldness may occur at the injection site. There is a negligible incremental risk of IMR measurement above those for PPCI. IMR measurement is expected to add no more than thirty seconds to screening time during a coronary angioplasty procedure. Having to screen for duration of thirty seconds long will increase radiation exposure by approximately 5% of the total PPCI radiation dose. Blood Sampling from arm: may cause bruising and discomfort.

Benefits to Society: this study will allow better understanding of antiplatelet function in patients with STEMI with potential benefits to future patients.

11. REGULATORY ISSUES

11.1 CONFIDENTIALITY

Blood samples will be anonymised with members of the research team at New Cross Hospital having access to the patient's details. All data collected on the patient will be stored in an anonymised fashion on fully encrypted password-protected computers at New Cross Hospital. The study will be archived for 5 years after the study has ended and then destroyed in line with the Research and Development Department policy.

11.2 SAFETY AND DATA MONITORING

Due to the nature of the study, data monitoring committee will not be required.

11.3 INDEMNITY

Standard NHS Indemnity is in place for this study.

11.4 SPONSOR

The Royal Wolverhampton NHS Trust will act as Sponsor for this Study.

11.5 FUNDING

Part funding is being successful. Further funding is being applied for.

11.6 AUDITS AND INSPECTIONS

The study will be audited and monitored by the sponsor's monitoring team.

11.7 TRAINING

The required training to undertake this project will be provided to members of the research team and the cardiac catheter lab nurses. An example is the administration of intravenous Cangrelor.



15 APPENDICES:

15.1 Appendix 1 – The Bleeding Academic Research Consortium (BARC) proposes 5 bleeding types (67)

- Type 0: no bleeding
- Type 1: bleeding that is not actionable and does not cause the patient to seek unscheduled performance of studies, hospitalization, or treatment by a healthcare professional; may include episodes leading to self-discontinuation of medical therapy by the patient without consulting a healthcare professional
- Type 2: any overt, actionable sign of haemorrhage (eg, more bleeding than would be expected for a clinical circumstance, including bleeding found by imaging alone) that does not fit the criteria for type 3, 4, or 5 but does meet at least one of the following criteria: (1) requiring nonsurgical, medical intervention by a healthcare professional, (2) leading to hospitalization or increased level of care, or (3) prompting evaluation
- Type 3
 - Type 3a
 - Overt bleeding plus haemoglobin drop of 3 to <5 g/dL* (provided haemoglobin drop is related to bleed)
 - Any transfusion with overt bleeding
 - Type 3b
 - Overt bleeding plus haemoglobin drop $\geq 5 \text{ g/dL}^*$ (provided haemoglobin drop is related to bleed)
 - Cardiac tamponade
 - Bleeding requiring surgical intervention for control (excluding dental/nasal/skin/haemorrhoid)
 - Bleeding requiring intravenous vasoactive agents

- Type 3c
 - Intracranial haemorrhage (does not include microbleeds or haemorrhagic transformation, does include intraspinal)
 - Subcategories confirmed by autopsy or imaging or lumbar puncture
 - Intraocular bleed compromising vision
- Type 4: CABG-related bleeding
 - Perioperative intracranial bleeding within 48 h
 - Reoperation after closure of sternotomy for the purpose of controlling bleeding
 - Transfusion of ≥5 U whole blood or packed red blood cells within a 48-h period[†]
 - \circ Chest tube output \geq 2L within a 24-h period
- Type 5: fatal bleeding
 - Type 5a
 - Probable fatal bleeding; no autopsy or imaging confirmation but clinically suspicious
 - Type 5b
- Definite fatal bleeding; overt bleeding or autopsy or imaging confirmation

Appendix 2: Study Summary Tables

	1	2	3	4	5	6	7	8
Timepoint reference	Prior to PPCI	First IC balloon inflation	End of PPCI (following the life-saving part)	90-120 minutes post PPCI	4 hours post dosing	24-36 hours post dosing (15 ml blood for VASP/VerifyNow and peak Troponin)	Discharge	Three months post PPCI
Eligibility	X							
Medical History	x							
Verbal Assent	x							
Randomisation	x							
Dispensation of treatment	Х							
Initiation of either oral Ticagrelor or IV Cangrelor therapy	X							
Written Informed consent			Х					
Demographic data collection	X							
10ml blood collection for VASP/ VerifyNow		×			X	X		
IMR			Х					
ECG				X				

10ml blood								
collection for						x		
Peak Troponin						^		
Level (routine)								
TIMI Flow			X					
Grade								
Vital Status assessment							X	Х
BARC definition for bleeding			x					
Target Vessel Failure			X					
CMR								Х
Concomitant Medications	X	X	X	X	x	X	X	Х
Adverse Events review	Х	X	X	X	X	X to stop at 36 hours		

Study Steps	Time
1-Quick initial assessment of patients suitable for enrollment in the trial	Upon arrival at the Heart and Lung centre, New Cross Hospital
2-Verbal assent	After the initial assessment
3-Randomisation to either one of the two trial treatment groups	After obtaining verbal assent
4-Initiation of either oral Ticagrelor or IV Cangrelor therapy	Based on randomisation result
5-Primary PCI procedure	Once the second antiplatelet therapy is initiated (Ticagrelor or Cangrelor)
6-Blood sampling for P2Y12 inhibition estimation (using VASP phosphorylation and VerifyNow tests)	A- At the time of first intracoronary balloon inflation (10 ml of blood from the femoral or radial sheath) B- 4 hours post dosing (10 ml of blood from an anticubital vein) C- 24-36 hours post dosing (15 ml in total. 10 ml for VASP/VerifyNow and 5 ml for peak Troponin level. One needle prick)
7-IMR measurement	Immediately following PPCI (same procedure setting)
8-Patient information sheet will be provided and written consent sought	After successful completion of PPCI
9-ECG recording to assess the degree of ST-segment resolution.	90-120 minutes post PPCI

10-Peak Troponin level assessment	24-36 hours post PPCI.
11-TIMI flow grade assessment	Post PPCI
12-Vital Status assessment	On discharge and at three months post PPCI
13-CMR estimation of final myocardial infarct size	At three months post PPCI

STUDY COSTS

CMR	100 scans @ reduced research rate £100	= £10,000
IMR estimation	100 pressure wires @ £300 Unit	= £30,000
Blood Tests	300 Verify now @ £38.78 per sample	=£11,634
	100 Troponin @ £9	= £900
	300 VASP @ £16 per sample	= £4,800
Drug Costs	50 doses Cangrelor	=£7500
Sponsor Monitoring	Costs	=£2,000
Travel/Presentation	= £2,000	
Total Cost		= £68,834

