4.1 STUDY OUTCOME MEASURES

a) Degree of platelet inhibition measured with VerifyNow TM rapid platelet function analyser and also VASP flow cytometry at infarct vessel open time (also known as balloon time), 4 and 24-36 hours post dosing.

b) Index of Microvascular Resistance (IMR) measurement using pressure wire studies immediately following the PPCI procedure.

c) Measurement of thrombolysis in myocardial infarction (TIMI) flow grade using TIMI Frame Count.

d) ST Segment Resolution by ECG at 90-120 minutes post PPCI.

e) Infarct size by Peak Troponin at 24-36 hours post PPCI.

f) Final infarct size by CMR at three months in both patient groups (total of 100 subjects).

This study is not powered for clinical outcomes; however clinical and safety data will be recorded.

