4.2 IN PATIENT SAFETY ENDPOINTS

- BARC definition for bleeding (see appendix 1)
- Target Vessel Failure
- Vital Status at Discharge

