5 PARTICIPANT ENTRY

5.1 CONSENT

Consent will be a two-stage process for patients undergoing PPCI for STEMI. Verbal assent will be brief prior to the PPCI and first blood sample, so as not to lead to a reduction in the quality of patient care (MI outcomes are related to the door to balloon time with PPCI). A

shortened patient information sheet will be read to the patient and if verbal assent is gained it will be recorded in the clinical notes and the site file. This is in line with NRES guidelines that suggest that patients admitted with STEMI are considered as unconscious patients initially.

Following emergency PCI and IMR measurement, when the patient is pain free and has been able to rest, a full patient information sheet will be proffered and written consent sought. If the patient does not want to be part of the trial, he or she will be withdrawn from the study and future tests will not be performed. Treatment will continue in accordance with clinical guidelines. The patients' participation in the trial will last for 3 months. At the end of three months a Cardiac MRI scan will be performed unless there are specific contraindications. Vital status will be determined on discharge and at three months when patients turn up to have their cardiac MRI scan. If a patient fails to attend Cardiac MRI scan appointment in three months' time, a telephone call will be made to the relevant GP to determine the vital status of the patients.

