5.6 WITHDRAWAL CRITERIA

Patients are able to withdraw from the trial if they wish without the need to provide reasons and without their care being affected or compromised. Patients who decide to withdraw their consent to participate in the study will have all samples collected up to the time of withdrawal disposed of in appropriate manner. All information collected on the patient for the purpose of the study will be erased. The withdrawal shall be recorded in the study patient identification log. The treatment of the patient will continue in accordance with clinical guidelines should the participant choose to withdraw or not. If a patient dies after obtaining verbal assent but before gaining a written consent, they will still be included in the study and data collected up to the time of death will still be used. Patients who will need administration of glycoprotein IIb/IIIa inhibitors during or post PPCI procedure and patients who fail to have Cangrelor or Ticagrelor for unexpected circumstances will be withdrawn from the study and their data will not be collected.

Safety stopping criteria:

A participant would be withdrawn from the trial if the Clinician feels that continued participation would be unsafe for the participant.

This could include, but not restricted to:

- An anaphylactic shock
- An SAE occurring

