6.2 Sampling and Dosing

6.2.1 Study subjects will have a $P2Y_{12}$ inhibitor administered (Ticagrelor or Cangrelor) after recorded verbal assent following randomisation. The time of loading dose will be recorded and the patient transferred to the cardiac catheterization suite. After the insertion of the radial or femoral sheath, 10 ml of whole blood will be drawn from this sheath at the first intracoronary balloon inflation time. A further 10 ml will be taken 4 hours post dosing (or as close as is practicable). Further sampling (15 ml) on the ward will take place 24-36 hours post dosing from an anticubital vein using a 21-gauge needle (see study summary tables). Samples taken will be analysed to assess $P2Y_{12}$ activity using VerifyNow TM (Accumetrics, San Diego, California, USA) and VASP Flow Cytometry tests. Peak Troponin levels will be assessed as well using the same blood samples.

6.2.2 Dosing: Patients will be divided into two arms; Oral Ticagrelor (50 patients) and Intravenous Cangrelor (50 patients) arms.

Ticagrelor arm: Patients will receive Ticagrelor 180mg loading dose on the cardiology ward prior to transfer to the catheter lab. Thereafter, a maintenance dose of 90mg twice daily will be given and continued for 12 months duration.

Cangrelor arm: Patients will receive Cangrelor administered at a rate of 30 micrograms/kg intravenous bolus followed immediately by 4 micrograms/kg/min intravenous infusion. The bolus and infusion will be initiated in the cardiac catheter lab prior to the PCI procedure and continued for at least two hours or for the duration of the procedure (to increase up to three hours), whichever is longer. 30 minutes prior to stopping Cangrelor infusion, Ticagrelor 180 mg will be given followed by 90mg twice daily maintenance dose continued for duration of 12 months. Cangrelor will be obtained directly from The Medicines Company, retained at the

pharmacy department at New Cross Hospital and issued by the pharmacy department for our clinical trial purposes only. Ticagrelor will be received by the pharmacy department and designated for our clinical trial purposes only.

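### BARC bleeding and target vessel failure are in-patient endpoints, but each is scheduled once, at end of PPCI, and nothing says that later bleeds are BARC-graded or captured from 36 hours to discharge

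*Combined protocol and SAP*

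**What the plan says.** Section 4.2, headed "IN PATIENT SAFETY ENDPOINTS", lists three items: bleeding by the BARC definition, target vessel failure, and vital status at discharge. It gives no assessment time for the first two.

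In Appendix 2 the row "BARC definition for bleeding" and the target vessel failure row are each marked only in column 3, headed "End of PPCI (following the life-saving part". Vital status is marked at discharge and at three months. Adverse event review is marked in columns 1 to 6, the last with the note "X to stop at 36 hours". The discharge column carries only vital status and concomitant medications. The list of study steps below the table has a step for vital status but none for bleeding or target vessel failure.

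Section 9.1.1 ends adverse event recording 36 hours after the index admission. Section 9.2 says that all SAEs are reported and gives no end time. Section 9.1.2 lists conditions that will not be classed as SAEs; they include transfusion and tamponade needing urgent surgery. Section 4.1 says that "clinical and safety data will be recorded", without saying when or how.

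**The concern.** An in-patient endpoint should be ascertained over the in-patient stay. Here the only scheduled assessment comes at the end of the procedure. Under section 6.2.2 the cangrelor infusion is "continued for at least two hours or for the duration of the procedure", whichever is longer, so that assessment can precede the end of the infusion.

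Three things are at stake. The reported bleeding and target vessel failure rates may cover only part of the stay. Bleeds in the adverse event log may never receive the BARC grade that the endpoint needs. Some serious bleeds after 36 hours may have no clear route into the data. Section 8 would end the trial early for unexpected excess bleeding with cangrelor, and section 7.1 says that the study will inform the power calculations of future studies, so the counts have a use beyond description.

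**Working it through.** The documents give no figure to reproduce on this point. The check sets the schedule beside the text, then sizes the effect of a missed event.

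**Marks in the eight columns of Appendix 2**

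| Row | Columns marked | Count |
|---|---|---|
| BARC bleeding | 3 | 1 of 8 |
| Target vessel failure | 3 | 1 of 8 |
| Adverse event review | 1 to 6, ending at 36 h | 6 of 8 |
| Vital status | 7, 8 | 2 of 8 |
| Concomitant medications | 1 to 8 | 8 of 8 |

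The BARC and target vessel failure marks align with those for IMR and TIMI flow grade, which the text also places at or just after the procedure. A cell merged across columns in the typeset table would alter this count and cannot be fully excluded. Columns 4, 5, 6 and 7 run from after the procedure to discharge and carry no mark for either endpoint.

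**To 36 hours.** Section 9.2.1 records all non-serious events, expected or not. Bleeds are therefore captured; what is missing is any statement that they are BARC-graded.

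**How much of the cangrelor period this covers.** Section 4 caps the infusion at three hours, and section 2.1 says that platelet function normalises within 60 minutes of stopping. 3 + 1 = 4 hours from the start of infusion. Recording to 36 hours leaves about 36 − 4 = 32 hours beyond that, less the time from admission to dosing. (Section 9.1.1 starts the clock at admission and Appendix 2 column 6 is timed from dosing; the difference is minor.)

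**From 36 hours to discharge.** Scheduled captures: BARC 0, target vessel failure 0, non-serious adverse events 0. SAEs may still be reported, but it is not stated whether the 36-hour stop applies to them.

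**The not-SAE list against Appendix 1.** Two of its nine items match BARC type 3 criteria:
- Tamponade needing urgent surgery falls under BARC 3b, which includes cardiac tamponade.
- Transfusion is BARC 3a when it accompanies overt bleeding. The match is partial. The list names the treatment, and the underlying bleed can still be an SAE if it is unexpected and, for example, life-threatening or prolongs the stay.

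The medical-judgement sentence in section 9.1.2 refers to other situations and may not override the list.

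**Size of one missed bleed at 50 per arm**
- Shift in an arm's rate: 1/50 = 2 percentage points.
- Clopper-Pearson 95% intervals: 0/50 gives 0 to 7.1%; 2/50 gives 0.5 to 13.7%.
- Fisher's exact test, two-sided, losing one bleed from the higher arm: 2 v 10 gives p = 0.028 and 2 v 9 gives p = 0.051, but 1 v 10 gives p = 0.008 and 1 v 9 gives p = 0.016.

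These event counts are illustrative; the documents give no expected bleeding rate.

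**The case against.** The strongest reply is that the cangrelor-specific risk is brief and already covered. Its effect should be over about four hours after the infusion starts, both arms are on ticagrelor afterwards, and every adverse event is recorded to 36 hours. A bleed logged without a grade can be graded later against Appendix 1. This stands, and it limits how much the gap weakens the section 8 rule on excess bleeding with cangrelor. It does not supply the missing statement that logged bleeds are graded, and it does not deal with target vessel failure.

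A second reply is that column 3 is meant loosely. Written consent sits there too, although section 5.1 seeks it "when the patient is pain free and has been able to rest", and the in-patient label may itself imply the whole stay. That may be the intention, but no later column or step carries it out.

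A third is that this is a pilot, not powered for clinical outcomes, and that section 7 does not name bleeding among the variables tested. That is correct and is a reason to give confidence intervals. It does not excuse partial ascertainment of endpoints that the protocol chose.

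A reader might go further and infer that a large share of bleeds would be lost, that power for bleeding would fall sharply, or that the committee would be blind to cangrelor bleeding. The documents support none of these. They give no bleeding rate, no timing of bleeds and no length of stay, and bleeds to 36 hours are recorded. The Fisher example that crosses 0.05 is a knife edge, as the second pair of counts shows.

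**Conclusion.** The point holds as an inconsistency between section 4.2, section 9.1 and Appendix 2, and it should be fixed. Followed as written, the plan grades bleeding and assesses target vessel failure once, at end of PPCI. It leaves bleeds to 36 hours without a stated grade and schedules nothing for either endpoint from then to discharge. After 36 hours the route into the data is unclear for tamponade needing urgent surgery, and for transfusion with overt bleeding where the bleed does not itself meet the SAE definition.

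The likely loss is modest for bleeding attributable to cangrelor. It is nil after 36 hours for patients already discharged; because length of stay is not given, the overall extent cannot be stated. Each missed bleed shifts an arm's rate by 2 percentage points and can change a test result. The direction of any bias cannot be told from the documents.

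The conclusion rests on reading the column 3 marks as they stand and on the absence of any other assessment time in the text.

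**What to change.** Reconcile sections 4.2, 9.1 and Appendix 2:

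- Add one mark at discharge for BARC bleeding and one for target vessel failure, each covering the whole stay since randomisation. One assessment at discharge is enough. The documents do not define target vessel failure, so add a definition at the same time.
- In section 9.1.1, extend the recording of bleeding events to discharge, and say whether SAE reporting continues after 36 hours.
- State that all recorded bleeds, including those in the adverse event log to 36 hours, are BARC-graded.
- Give counts of BARC types 3 to 5 by arm to the section 8 committee, including events on the not-SAE list. Their SAE status need not change. This matters because section 5.6 gives "An SAE occurring" as an example of a reason for withdrawal, so reclassifying them could bring more patients under that clause.
- Report bleeding by arm with confidence intervals alongside any Fisher's exact test.

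The cost is a few schedule marks and sentences, plus a little grading from notes and reporting of counts. No new visits or tests are needed.
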